### **10.7.1 Hematology**

Red blood cell count, hemoglobin, hematocrit, white blood cell count, differential white blood cell count (neutrophil, eosinophil, basophil, monocyte, lymphocyte), and platelet count

### **10.7.2 Blood biochemistry**

AST, ALT,  $\gamma$ -GTP, CRP, LDH, ALP, total protein, albumin, glycoalbumin, glucose, total cholesterol, total bilirubin, direct bilirubin, creatinine, BUN (before and after dialysis), Na, K, Cl, Ca, P, serum iron, UIBC, TIBC, TSAT, and ferritin

### **10.7.3 Endocrinology**

Testosterone, free testosterone, prolactin, TSH, FT3, FT4, intact-PTH, and antidiuretic hormone

## **10.8 Vital Signs (Blood Pressure, Pulse Rate, Body Temperature)**

Systolic blood pressure, diastolic blood pressure, pulse rate, and body temperature will be measured after a period of rest before the first dialysis each week (Monday or Tuesday). The date and result of measurement will be recorded in the case report form. The same testing device will be used in the same subject throughout the study period in principle.

## **10.9 Body Weight**

Body weight will be measured before the first dialysis of each week (Monday or Tuesday). The date and result of measurement will be recorded in the case report form. At the start of the screening period, body weight will also be measured after dialysis, and the date and result of measurement will be recorded in the case report form.

---

## 10.10 12-lead ECG

Before dialysis and blood sampling on the first day of each week (Monday or Tuesday), 12-lead ECGs will be obtained in the supine position after a period of rest, and the date of measurement and the assessment by the doctor will be recorded in the case report form. The same testing device will be used in the same subject throughout the study period in principle.

## 10.11 Dependency Assessment

The investigator or subinvestigator will interview each subject using the questionnaire shown in [Appendix 8](#) and record the result of the interview. The dependency assessment members will perform dependency assessment based on the questionnaire.

Details are stipulated in a separate procedure.

## 10.12 Pregnancy Test

In women of childbearing potential (those who have not undergone total hysterectomy or bilateral total ovariectomy and within 1 year of their last menstrual period), a pregnancy test (serum HCG) will be performed to determine whether the subject is pregnant or not. Pregnancy will be determined centrally at the laboratory testing facility. The presence or absence of collected samples and the presence or absence of pregnancy will be recorded in the case report form.

## 10.13 Adverse Events

An adverse event is defined as any unfavorable or unintended sign, symptom, exacerbation of a complication, or disease in a subject, whether or not considered related to the study drug. Exacerbation of any variable used for individual efficacy evaluations will not be regarded as an adverse event.

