## 1.2 Treatment of Pruritus in Hemodialysis Patients

Main treatments of pruritus in hemodialysis patients include topical therapy with moisturizers, such as milky lotion and cream, and with steroids, and topical or internal therapy with antihistamines and antiallergics. However, many patients have an inadequate response to these existing treatments such as topical and internal therapies, and these patients are treated with an oral KOR agonist, nalfurafine hydrochloride. This drug activates KOR in the central nervous system, thereby exerting antipruritic effects on pruritus refractory to existing treatments. Nalfurafine hydrochloride is effective in treating pruritus; however, because of the oral formulation, dialysis patients have to take a larger number of tablets, which increases the burden of these patients taking many oral drugs to treat their complications. In addition, dialysis patients may have difficulty in taking this drug because of their decreased salivary secretion and restricted fluid intake. Furthermore, nalfurafine hydrochloride activates KOR in the central nervous system and the gastrointestinal tract, thereby inducing adverse drug reactions, such as sleep loss and constipation, frequently.

Under these circumstances, patients with an inadequate response to existing treatments have hoped the development of a new treatment that relieves itching, is more convenient for use, and causes fewer adverse drug reactions.

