### 4.1.2.2 Secondary endpoints

- The Shiratori's severity criteria have been selected as an endpoint for pruritus, provided that they are used widely to assess the degree of itching by dermatologists in Japan and that they can also be used to assess sleep disorder because they use the effects on daily activities as the criteria for severity.
- Skindex-16 and 5-D itch scale have been selected as QOL endpoints for pruritus because they are used to assess the skin disease-related QOL.
- PGIC has been selected as an endpoint for treatment effects assessed by subjects.

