**10.13.1.3 Considerations for the recording of adverse events**

- 1) Any diagnosis identified from signs and/or symptoms will be recorded as an adverse event term. The laboratory abnormality, abnormal finding, or symptom associated with the adverse event will not be regarded as the adverse event.
- 2) If no diagnosis can be identified from signs and/or symptoms, the laboratory abnormality, abnormal finding, or symptom will be regarded as the adverse event.
- 3) A laboratory abnormality or abnormal finding will be regarded as an adverse event when it is regarded as a clinically significant variation or change by the principal investigator or subinvestigator. A clinically significant variation or change is defined as a laboratory abnormality or abnormal finding that requires a medical intervention or treatment or is considered to be a variation or change that exceeds the normal range of the subject's physiological variation by the principal investigator or subinvestigator.
- 4) Any laboratory abnormality or abnormal finding in a test at the start of the screening period will not be regarded as an adverse event.
- 5) Any disease, symptom, or finding that has been present since before the informed consent procedure will not be regarded as an adverse event.
- 6) Any exacerbation of a complication, preexisting symptom, or finding will be regarded as an adverse event. Exacerbation of a complication, preexisting symptom, or finding is defined as an exacerbation of a disease, symptom, or finding present before study participation considered to be greater than expected by the principal investigator or subinvestigator, or an increased frequency or an increased seriousness or severity of a seasonal or intermittent symptom or finding.
- 7) Any exacerbation after the start of study treatment of an adverse event that has occurred between the time of signing informed consent and the start of study treatment will be regarded as a new adverse event.
- 8) Any operation or treatment scheduled before the time of signing informed consent will not be regarded as an adverse event.
- 9) Any elective operation or treatment that will not alter the disease condition (e.g., dental implant, cosmetic surgery, or suture removal after skin suture at the request of the subject) will not be regarded as an adverse event. However, if any of these interventions causes a clinically significant finding or symptom, the event will be regarded as an adverse event.

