## 25. Appendices

### Appendix 1 NRS (numerical rating scale)

### Appendix 2 Shiratori's severity criteria

Severity	Daytime symptom	Nighttime symptom
4: Severe itching	Intolerable itch, not relieved by scratching but instead worsens. Cannot focus on work or study.	Can hardly sleep because of itch. Scratching all the time, but itch intensifies with scratching.
3: Moderate itching	Scratching even in the presence of others. Irritation as a result of itch, continuous scratching.	Wake up because of itch. Can fall asleep again after scratching, but continue to scratch unconsciously while sleeping.
2: Mild itching	Itch sensation is relieved by light, occasional scratching. Not too disturbing.	Feel somewhat itchy, but can obtain relief by scratching. Do not wake up because of itch sensations.
1: Slight itching	Feel itchy sometimes, but tolerable without scratching.	Feel slightly itchy when going to sleep, but do not need to scratch. Sleeping well.
0: No symptom	Hardly feel itchy or do not feel itchy at all.	Hardly feel itchy or do not feel itchy at all.

Source: Shiratori A, et al., Clinical Evaluation of Oxitamide for Pruritus—Multicenter, Double-blind Study—, Nishinohon Journal of Dermatology 1983;45:1042-51.

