**Appendix 4 Specific signs or symptoms**

- 1) Dizziness (e.g., lightheadedness, vertigo)
- 2) Syncope (e.g., fainting spells)
- 3) Palpitation (e.g., heart pounding)
- 4) Tachycardia (as per vital sign assessment)
- 5) Falls (including fractures due to falls)
- 6) Seizures (including convulsions)
- 7) Gait disturbance (e.g., unsteady gait, unsteady on feet while walking)
- 8) Mental status change (e.g., patient appears confused, spatially or temporally disoriented, forgetful)
- 9) Somnolence (e.g., patient appears sleepier, drowsy, sedated, groggy)
- 10) Mood changes (e.g., patient appears more anxious, agitated, aggressive, uncooperative, restless, withdrawn)

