**Appendix 5 Skindex-16**

During the past 1 week, how often have you been bothered by the following?

1. Skin itching
2. Skin burning or stinging
3. Skin hurting
4. Skin irritated
5. Persistence or recurrence of condition
6. Worry about condition (e.g., that it will get worse)
7. Appearance of skin
8. Frustration about skin
9. Embarrassment about skin
10. Annoyed about skin
11. Feeling depressed
12. Effect of skin on interaction with others (e.g., family members, friends, familiar people)
13. Effect of skin in desire to be with people
14. Skin making it hard to show affection
15. Effect of skin on daily activities
16. Skin making it hard to work/have enjoyment

No. 1 to 4 are categorized into questions concerning symptoms, No. 5 to 11 are categorized into questions concerning emotions, and No. 12 to 16 are categorized into questions concerning functioning. Patients choose one answer to each question from among 7 scales, where 0 indicates never bothered and 6 indicates always bothered.

Copyright holder for the Japanese version: Higaki Y (Tokyo Women's Medical University),  
Publisher: Medical Professional Relations K.K.

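### Protocol 10.13 takes worsening of efficacy variables out of adverse events with no exception for serious worsening, and item 6 of 10.13.1.3 says the opposite for preexisting symptoms

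*Protocol*

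**What the plan says.** Protocol 10.13 defines an adverse event broadly and then adds one exclusion: "Exacerbation of any variable used for individual efficacy evaluations will not be regarded as an adverse event". The sentence carries no condition on seriousness, severity, expectedness or timing.

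Protocol 10.13.1.3 gives the recording rules. Item 5 leaves out symptoms present since before consent. Item 6 brings their worsening back in: "Any exacerbation of a complication, preexisting symptom, or finding will be regarded as an adverse event". It defines such worsening as more than the investigator expected or, for a seasonal or intermittent symptom, an increase in frequency, seriousness or severity.

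Protocol 10.13.4 defines serious adverse events as those adverse events that meet one of six criteria, among them hospitalization. Notification of the sponsor within 24 hours (12.2.2) and follow-up of unresolved events (10.13.9) depend on that classification or on adverse event status. SAP sections 12.1.1 to 12.1.6 tabulate what has been recorded as an adverse event. The SAP neither repeats nor limits the exclusion, and its section 15 lists no change to it.

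**The concern.** Pruritus is the condition under study, the preexisting symptom of every subject, and the subject matter of the efficacy scales. It falls under both rules at once. A site that follows 10.13 records no adverse event when itch worsens; a site that follows item 6 does. The adverse event incidence compared between groups in SAP 12.1.1 then depends partly on which sentence the site followed.

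The larger stake is serious worsening. An event that is not an adverse event cannot become a serious one under 10.13.4, so the expedited route is never reached.

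**Working it through.** No figure in the plan bears on this point, so the check sets the rules side by side.

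**Inputs.** The exclusion (Protocol 10.13); the recording rule (10.13.1.3, item 6); the seriousness definition (10.13.4); notification (12.2.2) and follow-up (10.13.9); the event tables (SAP 12.1) and lists (SAP 12.6); the entry criteria (Protocol 5.1.1).

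**Step 1: who is in scope.** Inclusion criterion 6 requires a baseline mean NRS above 4.0, so all 86 + 86 = 172 planned subjects have itch as a preexisting symptom. Protocol 1.1 describes the itching in these patients as intermittent, so both limbs of the item 6 definition can apply.

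**Step 2: apply each rule to three cases.**

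| Case | Under 10.13 | Under item 6 |
|---|---|---|
| Itch worsens more than expected, not serious | Not an adverse event | Adverse event |
| Itch worsens and leads to hospitalization | Not an adverse event, so 10.13.4 is not reached: no 24-hour notice, no follow-up under 10.13.9, no entry in the SAP 12.1 tables or 12.6 lists | Adverse event, serious under criterion 3 of 10.13.4: 24-hour notice, written report within 3 days, tabulated and listed |
| New insomnia not attributed to itch | Adverse event by the first sentence of 10.13 | Not needed; already an adverse event |

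The first two cases give opposite answers. The third does not.

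**Step 3: can either rule be presumed to prevail?** If 10.13 prevails as the more specific rule, the contradiction goes away but the gap for serious worsening becomes definite. If item 6 prevails, the gap closes for worsening greater than expected, but the exclusion in 10.13 no longer means what it says. Neither reading leaves the text sound.

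**Step 4: what is still captured in the second case.** The diary runs daily to the end of follow-up, and SAP 11.1.2 summarizes the NRS through follow-up Week 1. Withdrawal because lack of efficacy poses an unacceptable risk is a discontinuation reason (Protocol 5.3.1, item 2) and is counted in SAP 8.2. These sources give a score and a reason for leaving. They do not give the seriousness, outcome and causality fields of Protocol 10.13.1, and they do not trigger notification.

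**The case against.** Keeping the disease under study out of the adverse event tables is a legitimate choice: otherwise lack of effect is counted as harm. Efficacy data already show worsening by group, and a separate diagnosis that arises with it is an adverse event under item 1 of 10.13.1.3. All of this stands. It supports the rule that a worse score alone is not an adverse event. It does not supply a seriousness exception or settle the conflict with item 6.

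A reader might infer more: that sleep loss and depressed mood can never be adverse events here, because the Shiratori criteria were chosen partly since "they can also be used to assess sleep disorder" and Skindex-16 includes "Feeling depressed". The documents do not support that. The night-time grades are tied to itch ("Can hardly sleep because of itch"), the 5-D sleep item asks about the impact of itching, and Protocol 10.6.2 frames Skindex-16 around itching. Insomnia or depression as a symptom or diagnosis still meets the first sentence of 10.13. Mood change is asked about weekly under 10.13.5 and Appendix 4, although it becomes an event of special interest only if the investigator deems it an adverse event. What remains is a risk that a site reads the exclusion too broadly. That risk is somewhat greater for sleep, because insomnia is not in Appendix 4 and the only sleep question outside the efficacy scales comes after the drug is stopped.

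Nor do the documents show sleep loss to be a reaction of the class. Protocol 1.2 describes one drug, nalfurafine, as "inducing adverse drug reactions, such as sleep loss and constipation, frequently", and attributes this to receptor activation in the central nervous system and the gut. Protocol 1.3 describes MR13A9 as having limited central penetration, and the MR13A9 reaction lists in 1.3.2.2 and 1.4.1 name somnolence, not insomnia.

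**Conclusion.** The point holds as an unreconciled contradiction between Protocol 10.13 and item 6 of 10.13.1.3, together with a missing seriousness exception. As written, itch worsening that meets a seriousness criterion can stay out of expedited notification and out of the adverse event and serious event tables, though not out of the trial data.

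Its reach is every enrolled subject. Its frequency is unknown: the documents give no rate of serious itch worsening, and none of sleep loss on MR13A9, so any count would be a guess. The primary endpoint, its analysis and the sample size are unaffected.

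The conclusion assumes that no separate site procedure already settles the matter. The protocol refers to such procedures, for example in 10.13.5 and 19.1, but they are not among the documents.

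**What to change.** Replace the exclusion in Protocol 10.13 with a paragraph that states three things:

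- A worse NRS, severity-criteria, Skindex-16, 5-D or PGIC score is not by itself an adverse event.
- Itch worsening that meets a seriousness criterion in 10.13.4 is recorded as an adverse event and as a serious adverse event.
- Sleep or mood symptoms not attributed to itch are recorded as adverse events in their own right.

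Add a cross-reference in item 6 of 10.13.1.3 saying which rule governs itch worsening that is greater than expected but not serious, so that all sites treat it alike.

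The exception should not extend to all itch worsening in the follow-up period. That would have no threshold, and subjects who complete the study reach follow-up after open-label MR13A9, with no concurrent placebo group. Return of itch after stopping the drug would then be counted as harm.

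The cost is one protocol paragraph, a cross-reference, a site instruction and a few more adverse event records. Sample size, power and significance level do not change.

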### 10.13.1 Collection of adverse events

Adverse event information to be recorded in the case report form will include adverse event term, date of onset, date of resolution (when the outcome of an adverse event is resolved, resolved with sequelae, or fatal), severity, seriousness assessment, action taken with study treatment and other actions taken, outcome, causal relationship with study treatment, and assessment of adverse events of special interest. For any adverse event reported between the time of signing informed consent and the start of study treatment, adverse event term, seriousness assessment, and assessment of adverse events of special interest will be recorded in the case report form.

#### 10.13.1.1 Adverse event collection period

Adverse events will be collected between the time of signing informed consent and the end of the follow-up period.

#### 10.13.1.2 Adverse event interview

When interviewing each subject about his/her condition, the principal investigator or subinvestigator will pay due attention not to influence spontaneous reporting from the subject; for example, asking a general question such as "How have you been doing since the previous visit?"

**10.13.1.3 Considerations for the recording of adverse events**

- 1) Any diagnosis identified from signs and/or symptoms will be recorded as an adverse event term. The laboratory abnormality, abnormal finding, or symptom associated with the adverse event will not be regarded as the adverse event.
- 2) If no diagnosis can be identified from signs and/or symptoms, the laboratory abnormality, abnormal finding, or symptom will be regarded as the adverse event.
- 3) A laboratory abnormality or abnormal finding will be regarded as an adverse event when it is regarded as a clinically significant variation or change by the principal investigator or subinvestigator. A clinically significant variation or change is defined as a laboratory abnormality or abnormal finding that requires a medical intervention or treatment or is considered to be a variation or change that exceeds the normal range of the subject's physiological variation by the principal investigator or subinvestigator.
- 4) Any laboratory abnormality or abnormal finding in a test at the start of the screening period will not be regarded as an adverse event.
- 5) Any disease, symptom, or finding that has been present since before the informed consent procedure will not be regarded as an adverse event.
- 6) Any exacerbation of a complication, preexisting symptom, or finding will be regarded as an adverse event. Exacerbation of a complication, preexisting symptom, or finding is defined as an exacerbation of a disease, symptom, or finding present before study participation considered to be greater than expected by the principal investigator or subinvestigator, or an increased frequency or an increased seriousness or severity of a seasonal or intermittent symptom or finding.
- 7) Any exacerbation after the start of study treatment of an adverse event that has occurred between the time of signing informed consent and the start of study treatment will be regarded as a new adverse event.
- 8) Any operation or treatment scheduled before the time of signing informed consent will not be regarded as an adverse event.
- 9) Any elective operation or treatment that will not alter the disease condition (e.g., dental implant, cosmetic surgery, or suture removal after skin suture at the request of the subject) will not be regarded as an adverse event. However, if any of these interventions causes a clinically significant finding or symptom, the event will be regarded as an adverse event.

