### 8.2.3 Extension period

In addition to the use of conditionally permitted concomitant medications (e.g., anti-itch drugs) used at the start of the screening period, the study drug will be injected into the venous line of the dialysis circuit at the end of each dialysis session for 52 weeks (3 times weekly, 156 times in total). Study treatment in the extension period will be started at Week 6. The dose of the study drug will be determined according to [Table 8.2.2-1](#), and the dose of the study drug from Week 6 to immediately before Week 34 will be determined based on the subject's dry weight before dialysis at Week 6. The dose of the study drug after Week 34 will be determined based on the subject's dry weight before dialysis at Week 34. The study drug will not be administered at Week 58.

If any dialysis circuit trouble precludes injection through the dialysis circuit, the study drug will be administered directly intravenously. If an extra fourth dialysis session is required within the week, the study drug will be administered (up to 4 times weekly). If only the extracorporeal ultrafiltration method is used, the study drug will not be administered.

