**10.13.2 Date of onset of adverse events**

- Day when the subject, principal investigator or subinvestigator becomes aware of the sign or symptom of an adverse event
- Day when the subject, principal investigator or subinvestigator becomes aware of the exacerbation of a complication, preexisting symptom, or finding
- Day of confirmed diagnosis of an asymptomatic disease, of which time of onset can be estimated
- Day of a test that yields a laboratory abnormality or abnormal finding considered to be a clinically significant variation or change by the principal investigator or subinvestigator

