### 10.13.3 Severity of adverse events

The severity of adverse events will be categorized into 3 grades according to [Table 10.13.3-1](#). For an adverse event in which the severity changes, the highest severity will be recorded.

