#### **14.6.1 Adverse events and adverse drug reactions**

For the double-blind period, analysis will include events occurring between the start of study treatment in the double-blind period and the end of the double-blind period. For the entire study period, analysis will include events occurring between the start of study treatment in the double-blind period and the end of the follow-up period.

Adverse events of special interest will also be summarized in the same manner.

1) Incidence of adverse events and adverse drug reactions

The number of events, the number of subjects experiencing events, the incidence of events and its two-sided 95% confidence interval will be presented. For the double-blind period, a Fisher's exact test will be used for comparisons between the placebo group and the MR13A9 0.5 µg/kg group, and the between-group difference in incidence and its 95% confidence interval will be presented.

2) Incidences of adverse events and adverse drug reactions (serious events and events leading to discontinuation)

The numbers of events, the numbers of subjects experiencing events, and the incidences of events will be presented for all events, events leading to death, serious events other than death, and events leading to discontinuation.

3) Occurrence of adverse events and adverse drug reactions

The number of subjects experiencing events and the incidence of events will be presented for all events and by primary SOC and PT.

4) Occurrence of adverse events and adverse drug reactions (by severity)

The numbers of events by severity will be presented for all events and by primary SOC and PT.

5) Occurrence of adverse events and adverse drug reactions (by time of onset)

For the entire study period, the number of subjects experiencing events and the incidence of events for all events and by primary SOC and PT will be presented by time of onset.

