5.7.1 Handling of data in tabulation at each time point (excluding symptom diary

data)

- Data will be summarized by time point according to the time windows shown in [Table 5.7.1-1](#). Data obtained outside the time windows will be excluded from tabulation at each time point.
- If multiple data are available within the time window, the data obtained at scheduled visit will be employed.
- Data for observations and tests performed at unscheduled visits or 10 days after the day of the final dose will be excluded from the tabulation.
- For dependency assessment, all data collected will be employed regardless of the time window.

Table 5.7.1-1 Time windows for assessment time points

Assessment time point	Scheduled date ^{a)}	Time window
At Week -2	-14	Scheduled date \pm 3 days
At baseline	1	Day -3 to Day 1
At Weeks 1 to 12	$7 \times x + 1^b)$	Scheduled date \pm 3 days
At Weeks 18 to 58	$7 \times x + 1^b)$	Scheduled date \pm 7 days

a) The start of study treatment in the double-blind period is defined as Day 1 and the day before the start of study treatment as Day -1.

b) x: Number of weeks

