12.1 Adverse Events and Adverse Drug Reactions

Unless otherwise specified, the following events will be tabulated.

- Double-blind period
 - Events occurring between the start of study treatment and the end of the double-blind period
 - Adverse events of special interest occurring between the start of study treatment and the end of the double-blind period
- Entire study period
 - Events occurring between the start of study treatment and the end of the follow-up period

- Events occurring between the start of study treatment and the end of the extension period
- Adverse events of special interest occurring between the start of study treatment and the end of the follow-up period
- Adverse events of special interest occurring between the start of study treatment and the end of the extension period

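### An adverse event that starts on placebo and worsens after the Week 6 switch to MR13A9 stays one record with a placebo-period onset at its highest severity, and no MR13A9-onset event is recorded

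*Protocol*

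**What the plan says.** Protocol 10.13.1.3 has two rules on worsening. Rule 7) is worded for "Any exacerbation after the start of study treatment of an adverse event that has occurred between the time of signing informed consent"; the interval closes at the first dose, and such a worsening becomes a new adverse event. Rule 6) covers complications and preexisting symptoms or findings, defined as "an exacerbation of a disease, symptom, or finding present before study participation" that worsens more than expected, or as a seasonal or intermittent symptom that becomes more frequent, serious or severe.

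Protocol 10.13.2 dates an event from the "Day when the subject, principal investigator or subinvestigator becomes aware of the sign or symptom of an adverse event". A worsening has its own onset date only for a complication or a preexisting symptom or finding. On grading, Protocol 10.13.3 says: "For an adverse event in which the severity changes, the highest severity will be recorded".

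SAP 5.7.1 fixes the clock: "The start of study treatment in the double-blind period is defined as Day 1". Protocol 8.2.3 gives the switch: "Study treatment in the extension period will be started at Week 6". Figure 8.1-1 shows placebo subjects moving to MR13A9 at that point.

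For the double-blind tables, Protocol 14.6.1 says that "analysis will include events occurring between the start of study treatment in the double-blind period and the end of the double-blind period", and SAP 12.1 lists "Events occurring between the start of study treatment and the end of the double-blind period". Protocol 14 and SAP 4 limit the double-blind analysis to data up to the end of that period.

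**The concern.** Rule 7) accepts that worsening after first exposure deserves its own record. It applies that principle once, at the first dose of the double-blind period. For half the randomised subjects that dose is placebo, and their first exposure to MR13A9 comes six weeks later with no equivalent rule.

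What is at stake is the safety picture of early MR13A9 exposure in the P-MR group. Protocol 8.2.5 reports that in Study MR13A9-4 all adverse drug reactions occurred before Week 6 of treatment. For P-MR subjects the comparable early window opens at the switch, and there a worsening of an ongoing event leaves no separate trace by onset. A second, conditional risk is that a grade reached in the open-label phase enters a randomised severity table.

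**Working it through.** **Step 1: the day boundary.** SAP Table 5.7.1-1 gives scheduled day = 7 × x + 1. Week 6 is 7 × 6 + 1 = 43. Weeks 12, 24, 36 and 48 give 85, 169, 253 and 337. All five match the cut-offs in SAP Table 12.1.5-2. The < 6 weeks category (< 43 days) is thus onset before the scheduled switch.

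**Step 2: which rule reaches an event that began on placebo and is still ongoing at Week 6?**
- Rule 7): no. The event arose after the start of study treatment.
- Rule 6): no for a continuous event, which was not present before participation. Its seasonal or intermittent wording might reach some events that come and go.
- Protocol 10.13.2: no new onset date, because the event is neither a complication nor preexisting as rule 6) defines it.
- Protocol 10.13.3: one severity is kept, the highest.

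An event that resolves and recurs after Week 6 would presumably be a new event. The gap concerns events still ongoing at the switch.

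**Step 3: an assumed example.** A placebo subject has a mild event on Day 30 that becomes severe on Day 50, after the first MR13A9 dose. Time to onset (SAP 7) is 30 − 1 + 1 = 30 days.

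| | As written | If worsening after the switch were a new event |
|---|---|---|
| Records | 1 | 2 |
| Onset | Day 30 | Day 30; Day 50 |
| Severity | severe | mild; severe |
| Onset category | < 6 weeks (and < 12) | first: < 6 (and < 12); second: < 12 only |
| Record with onset on MR13A9 | none | one |

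**Step 4: where it shows in the tables.**
- Double-blind incidence (SAP 12.1.1): one placebo subject with an event, under either rule.
- Double-blind severity (SAP 12.1.4): mild if the Week 6 grade is used, severe if the single field has been updated and is used as it stands. The same holds for an event that starts on MR13A9 and worsens in the extension.
- Entire-study severity: one severe event under P-MR as written, against one mild and one severe.
- Onset table (SAP 12.1.5): not split by severity. The < 12 weeks row includes the < 6 weeks row, so for the same preferred term the subject count in < 12 is the same either way. A worsening on Day 200 would differ: as written nothing appears after the < 12 row, whereas a new event would fall in the 24 to < 36 weeks row.

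**Step 5: scale, on assumptions only.** The documents give no rate. Suppose 30–50% of the 86 placebo subjects have an event, 20–40% of those are ongoing at Week 6, and 10–20% of those worsen on MR13A9. The low end is 86 × 0.30 × 0.20 × 0.10 = 0.5 subjects and the high end is 86 × 0.50 × 0.40 × 0.20 = 3.4. This treats all 86 as entering the extension and counts any degree of worsening. It illustrates how many records might be affected and does not estimate a bias.

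**The case against.** The strongest reply is that the randomised tables are already protected. Protocol 14 and SAP 4 cut the double-blind analysis at the end of that period, and data handling is settled before lock. On that text a grade reached in the extension does not belong in the placebo column. This largely stands: a reader might infer that placebo severity is inflated, but that happens only if the field is updated before lock and used unchanged. What the text lacks is a way to recover the earlier grade. The lock waits for all double-blind data (Protocol 14.7), by which time early subjects may be well into the extension.

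Three further inferences are tempting and not supported.
- That the gap favours MR13A9 in both the randomised and the extension tables. Any leakage could affect both arms, because an MR13A9 event worsening in the extension would carry its later grade in the same way. The net sign is unknown.
- That double-blind tables produced before and after the worsening would disagree. Only one double-blind lock and analysis is planned (Protocol 14.7, SAP 6.3.1).
- That the affected count can be set against the overseas phase III adverse drug reaction rates of 6.9% and 5.3%. These subjects already had an event on placebo, so overall placebo adverse event incidence does not change.

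Nor is the worsening lost altogether. Entire-study tables carry it under P-MR at the highest grade, special-interest signs are asked about weekly (Protocol 10.13.5), and serious events and events leading to interruption or discontinuation are listed by subject (SAP 12.6). Protocol 10.13.3 governs severity only, and the separate case report form procedure is not available; it might say more about seriousness and action. None of this supplies an onset on MR13A9.

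**Conclusion.** The gap is real and should be closed. Followed as written, the recording rules give worsening on first MR13A9 exposure a placebo-period onset, and the P-MR group shows no MR13A9-onset event for it. That conclusion needs no numerical assumption. It applies to continuous events ongoing at the switch, and the attribution problem is confined to P-MR because MR-MR subjects do not change treatment at Week 6.

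Entry of post-switch severity into the double-blind tables is a possibility in either arm that depends on when the field is updated. Size and net direction cannot be derived from the documents. The primary analysis and the overall placebo adverse event incidence are not affected.

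**What to change.** Extend rule 7) of Protocol 10.13.1.3, for both groups: any worsening after the first extension-period dose of an adverse event with onset before that dose is recorded as a new adverse event, and the existing record keeps the severity, seriousness and action reached before that dose. Put the same instruction in the case report form guidance. In SAP 12.1, state that double-blind tables use severity, seriousness and action up to the first extension dose.

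The cost is one protocol sentence, one form instruction, one SAP sentence and a few extra adverse event records. Applying the rule in both groups keeps recording symmetric. The change corrects the records; the cumulative < 12 weeks row of the onset table would still pool placebo and early MR13A9 exposure for P-MR subjects.
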